#### Visit 10 (Day 125-150)

This visit will be scheduled between approximately 125-150 days, approximately 3-4 months post 2nd transfusion to test biotin antibodies in MUH-CTRC.

- Vital signs (Temp, HR, RR, BP, pulse ox)
- Blood draw to determine BioRBC survival.
- Blood draw to test antibodies to BioRBCs.
- Blood draw for clinical lab testing (CBC)
- AE assessment

Total blood volume drawn will be about 1 tablespoon (approximately 12mls).

#### Additional blood draws

Following the transfusion visits, subjects may be asked to return periodically over the next 3 months for further blood draws important for the biotinylation analysis of the their blood cells. The total volume will not exceed 20ml. Subjects will be compensated each time needed to return to MUH for a blood draw.

## **2.3 INVESTIGATIONAL PRODUCT**

The investigational product is Biotinylated Red Blood Cells (BioRBCs). We will use sulfo-NHS-biotin to label human RBCs with biotin. Sulfo-NHS-Biotin is supplied in pre-weighed 1mg microtubes (EZ-Link Sulfo-NHS-Biotin, Thermo Scientific, Rockford, IL, USA) as a lyophilized white powder and is stored at -20°C.

**Dosages:** The dose of biotinylated red blood cells is designated by the concentration of biotin ( $\mu\text{g/mL}$ ) used to label them. The actual total dose of biotin delivered per product is a function of the labeling dose (3 or 15  $\mu\text{g/mL}$ ) and labeling efficiency (approximately 1%), as all free biotin is washed from the product. The labeling efficiency will be determined for each product by quantitative flow cytometry. In our scale-up studies, RBC product labeled at 30  $\mu\text{g/mL}$  contained a total biotin dose of  $54.8 \pm 34.0$   $\mu\text{g}$  biotin/product (mean, SD). Biotinylated autologous RBCs labeled at 15  $\mu\text{g/mL}$  will be administered intravenously on day 5-7 in a volume of approximately 150 mL (0.5 - 1% of the subject's total intravascular volume). The subject will again receive BioRBCs labeled at 3  $\mu\text{g/mL}$  on day 35-42 intravenously. As most of the biotin is washed away during labeling, the total biotin dose subjects will receive is approximately 27.5  $\mu\text{g}$  during the first transfusion and 5.5  $\mu\text{g}$  biotin during the second transfusion. The BioRBCs will circulate in the subject's bloodstream for the lifespan of the cells (approximately 120 days). Two separate infusions of BioRBCs over a period of 5-6 weeks will result in exposure to BioRBCs for 5-6 months (approximately 165 days).

Quantitative Estimation of Total Biotin Dose: For each batch of biotin labeled RBC, we perform quantitative flow cytometry to determine the average number of molecules of biotin per conjugated RBC and estimate the total dose of biotin administered to the patient. Biotin is quantified by labeling the biotin-conjugated cells with titrated Phycoerythrin (PE)-conjugated streptavidin and

measuring the PE mean fluorescence intensity of the labeled RBC by flow cytometry. The Mean Fluorescence Intensity (MFI) of the labeled RBC is interpolated on a calibration curve derived from PE-conjugated beads (blank and 4 levels of PE) with known numbers of PE molecules per bead (Quantum R-PE MESF beads, Bangs Laboratories). The results are reported as molecules of Mean Equivalent Soluble Fluorescence (MESF) per labeled RBC. Under carefully controlled labeling conditions, MESF/RBC can be interpreted as molecules of biotin/RBC. The total dose of biotin delivered to the patient may then be estimated as follows:

$$1) \text{ Total Biotin Molecules} = \text{MESF/RBC} \times \text{total RBC}$$

$$2) \text{ Total Biotin (mol)} = \frac{\text{Total Biotin Molecules}}{6.02 \times 10^{23}}$$

$$3) \text{ Total Biotin Dose (g)} = \text{Total Biotin (mol)} \times 244.31 \text{ (formula weight of biotin).}$$

### Determination of molecules of equivalent soluble fluorochrome (MESF)

We determined MESF for 16 independent samples (labeled at 2 biotin concentrations). Sulfo-NHS-biotin labeling concentration ( $\mu\text{g/mL}$  total reaction mixture) correlated with MESF but there was more variability at the lowest dose ( $3 \mu\text{g/mL}$ ).

There are 3 sequential independent products labeled at 3 and  $30 \mu\text{g}$  biotin/mL total reaction mixture. Calibration of the results in MESF shows that RBC-bound biotin of RBC labeled at the same sulfo-NHS-biotin concentration, using the same cGMP-compliant procedure could vary by more than 2-fold. Despite the variability, excellent separation was obtained between unlabeled RBC and RBC labeled at the two biotin concentrations.

#### **2.3.1. Investigational Product Preparation and Dispensing**

The packed RBCs will be biotin-labeled under sterile conditions by trained personnel at the UPMC Hematopoietic Stem Cell Laboratory (HSCLab), an International Organization for Standardization Class 7 (ISO7) Current Good Manufacturing Practice (cGMP) compliant facility. The HSCLab has a Master file on file with the FDA that is cross referenced by this protocol. Preparation of the biotin solution and filter sterilization occurs immediately before addition to the autologous red blood cell sample, which is handled under sterile conditions. The sterile biotin reagent and autologous RBCs are combined at a constant rate and are incubated at room temperature for 30 minutes to allow biotin to bind to the surface of the RBC membrane. After the incubation period, the product is washed and re-suspended in saline with 5% human serum albumin. A BioRBC sample is removed by sterile technique for release testing. Release criteria include a final RBC packed cell volume  $\geq 25 \text{ mL}$  and total endotoxin content of  $< 5 \text{ EU/kg}$  recipient actual body weight. The product will be withheld if either of these criteria is not met. Additional product quality testing will include quantitative flow cytometry to determine the actual dose of biotin in each product, and pre- and post labeling 14 day aerobic, anaerobic and fungal sterility cultures.

The biotinylated autologous RBCs will be provided in 300 mL transfer bags for infusion, at a volume of  $\sim 150 \text{ mL}$  and a hematocrit of approximately 35% to 40%. The HSCLab is (Foundation for the Accreditation of Cellular Therapy (FACT) accredited and uses International Society of Blood Transfusion (ISBT) 128 Standard Terminology for Blood, Cellular Therapy, and Tissue

Product Descriptions labeling and packaging, according to Good Clinical Practice and regulatory requirements. HSCLab will dispense the BioRBC product upon receiving a signed and dated physician's processing request form. The HSCLab will maintain accurate records of investigational products including subject dispensing, product destruction and documentation of adequate storage of investigational products.

Further details on investigational product preparation and dispensing are provided in a separate laboratory standard operating procedure.

### **2.3.2. Administration of Investigational Product**

BioRBCs will be administered intravenously on two separate occasions (5-7 and 35-42 days following donation). BioRBCs will be transfused at a rate of 100-150 mL/hr. This range will allow us to reduce infusion rate if recipient complains of any discomfort or pain. Recipient vitals will be taken at baseline and approximately every 15 minutes during the infusion and then approximately 15 minutes after the infusion ends by qualified personnel at the Clinical Translational Research Center (CTRC) of UPMC Montefiore Hospital.

### **2.3.3. Dose Selection**

Experience with biotin labeling method to study RBC survival in humans is expanding. Biotinylated RBCs (BioRBCs) were first used to study RBC survival in rabbits in 1987. Since then, the use of BioRBCs has successfully been expanded to human studies evaluating RBC 24-hour recovery and lifespan. Investigators have used BioRBCs to study RBC volume and survival in healthy adults. BioRBCs have also been used in patients with sickle cell disease to study autologous RBC survival and post-infusion membrane changes, and it is currently being used to study both autologous and allogeneic RBC survival in neonates in the intensive care unit. The primary safety concern in using the BioRBC method in humans is the potential formation of antibodies against the BioRBCs. The formation of anti-BioRBC antibodies was observed in 3 subjects out of 20 adults studied (15%). The anti-BioRBC antibodies appeared 4-5 months after the infusion of BioRBCs, reacted only against BioRBCs (i.e. antibodies did not behave as autoantibodies), did not affect BioRBC 24-hour recovery or survival, and were transient in nature (i.e. anti-BioRBC antibody activity disappeared within 1-4 months after initial detection).

Biotin has also been directly administered to healthy adults both orally and intravenously with daily oral doses being as high as 2000 µg and IV doses as high as 4500 µg without any reported adverse effects. In this study, subjects will receive a total biotin dose of approximately 0.2 µg/ml (27.5 ug biotin) during the first transfusion visit and 0.04 µg/ml biotin (5.5 ug of biotin) during the second transfusion visit.

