
Study Aims:
	
Aim 1: To explore the effect of selected SNPs on in-vitro measures of red cell biophysical properties, storage integrity, and post-autologous transfusion RBC recovery.
 
Aim 2: To examine the relationship between sex and sex hormones (testosterone) and in vitro markers of storage integrity and the in vivo 2-4 hours recovery and survival of RBCs stored under standard blood banking conditions.

Study Design:
	
The proposed clinical investigation will evaluate the in vivo lifespan of RBC in healthy volunteers after autologous transfusion over two different periods of storage. We will collect blood samples and label them with a naturally occurring vitamin, biotin. The RBCs will then be re-infused back into the same participant at 2 time points (5-7 days and 35-42 days after storage).
 
To evaluate RBC post transfusion survival, blood samples will be taken to quantify biotin labeled RBCs at 2-4 hours, 1 month and 2 months after each transfusion. On Day 125-150 post blood donation, subjects will be followed to evaluate anti-biotinylated RBC antibody formation. Throughout the study, subjects will be monitored carefully for occurrences of adverse events, laboratory test abnormalities, and changes in vital signs.
 
This protocol may cover up to (9) separate but similarly designed studies that may test 8 groups with candidate SNPs that were associated with hemolysis in REDS III Omics GWAS studies. Candidate SNPs may include, but are not limited to sickle cell trait (AS), and single nucleotide polymorphisms (SNPs) in ankyrin 1 (ANK1), glucose-6-phosphate dehydrogenase X-linked (G6PD), piezo-type mechanosensitive ion channel component 1 (PIEZ01), spectrin alpha (SPTA), and extended synaptotagmin-like protein 2 (ESYT2), Myo9B and SEC14. A subset of recalled donors with these SNPs will be asked to provide a blood sample to be tested for functional effects on red cell biophysical properties, stability in storage, and release of eDAMPs, and compared to donors with no implicated SNPs. We will develop an enriched SNP profile that defines a high risk and a low risk donor for further evaluation in autologous reinfusion studies as a low cost precision transfusion medicine array.
 
A 9th group of subjects on testosterone replacement therapy will also be evaluated.

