#### Visit 8 (Day 65-72)

This visit will be scheduled between approximately 65-72 days, approximately 2 months post 1st transfusion or 1 month post 2nd transfusion in MUH-CTRC.

- Vital signs (Temp, HR, RR, BP, pulse ox)
- Blood draw to determine BioRBC survival.
- Blood draw to test antibodies to BioRBCs.
- Blood draw for clinical lab testing (CBC)
- AE assessment

Total blood volume drawn will be about 1 tablespoon (approximately 12 mls).

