### **2.3.4. Testing for Antibodies to BioRBCs**

On Day 0, plasma samples will be obtained to test subject's naturally occurring anti-BioRBC antibodies. On Day 32-41 and Day 125-150, plasma samples will be obtained from the subjects. These plasmas will be tested for anti-BioRBC antibodies using a commercial sensitive and specific IgG gel card agglutination assay.

The gel card assay is based on RBC agglutination. The gel cards will be used according to the manufacturer's recommendations (MTS Anti-IgG Card, MTS084024, Ortho Clinical Diagnostics, Rochester, NY). Briefly, 50 µL of the target BioRBC-N or unlabeled RBC (at 0.8% hematocrit in

Diluent 2) are prepared from a group O+ convenience donor and layered atop the buffer in gel card microtubes. Test plasma (25 µL) is added to the target BioRBC or RBC in the gel column and incubated at 37°C for 30 min (ID-MTS Incubator MTS9680 (Ortho Clinical Diagnostics, Rochester, NY). Gel cards are subsequently centrifuged at 895 RPM (80-90 RCF) for 10 min (ID-MTS Centrifuge MT515060, Ortho Clinical Diagnostics, Rochester, NY). The presence of BioRBC agglutination is quantified using the manufacturer's gradation-specific definitions of reactivity. Reactivity scores range from 0 (no agglutination) to 4+ (agglutinates are trapped on the surface of the gel bed).

Detailed testing procedures are provided in a separate laboratory standard operating procedure.

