## **6. POTENTIAL RISKS AND BENEFITS**

## 6.1 POTENTIAL RISKS

As with any experimental procedure, there may be adverse events or side effects that are currently unknown, and certain of these unknown risks could be permanent, severe or life threatening. Every attempt will be taken to minimize these risks.

Risks of BioRBC Infusion: The risks of BioRBC infusion include the possibility that the biotinylated cells may be destroyed and cleared from the circulation. The amount of transfused BioRBCs represents about 2% of the total blood volume in the subject and removal of the BioRBCs are not likely to cause any health problems. During the biotinylation process, the autologous RBCs will be removed from the blood bank and processed under a sterile tissue culture hood. The biotinylation process will be performed in a GMP cellular therapy facility; however there is a minimal risk of bacterial contamination. This risk is reduced by requiring that each BioRBC sample be tested for and passes endotoxin contamination testing prior to infusion.

Risk of Antibody Formation: In a previous study in which adults were transfused with BioRBCs, 3 of 20 (15%) subjects developed antibodies to BioRBCs, but none developed anemia or any other health problems. In study subjects that developed antibodies, the antibodies disappeared from the blood over a period of months. To reduce this risk of antibody formation, a lower dose of biotin will be used throughout this study compared to the previous study, and subjects will be screened for antibody formation throughout the study and during follow-up visits. In summary, we do not anticipate side effects in the proposed biotin doses.

Rare risks include immune-mediated hemolytic reaction to transfused biotinylated RBCs. Given the small volume of BioRBC infused, no significant clinical effects of hemolysis of biotinylated RBC is expected.

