#### **6.4.8. Withdrawal of Subjects and Stopping Criteria:**

##### **STOPPING RULES:**

**Withdrawal of Subjects:** Subjects must be withdrawn from the study for the following reasons:

- An SAE or a serious post-infusion hemolytic event that is determined to be possibly, probably, or definitely related to the infusion of autologous BioRBC.
- Detection of anti-BioRBC antibodies following first infusion. In the unlikely event that a study subject tests positive for bioRBCs following first infusion, the subject will be withdrawn from

the study. The subject will not receive the subsequent RBC infusion. Since anti-BioRBC antibodies attack BioRBCs, the 2-4 hours post transfusion survival and mean lifespan measurements will be affected. Based on the time of discovery, the 2-4 hours time point measurement may be retained or discarded. The participant will be followed for signs and symptoms of hemolysis as well as the disappearance of the anti-biotinylated RBC antibodies.

Subjects may be withdrawn from the study for the following reasons:

- In the unlikely event that a stored unit does not pass the endotoxemia test, red blood cells will not be transfused and will have to be withdrawn from the study.
- In the event that a donated RBC unit is misplaced, the subject's participation in the study will be terminated since an autologous transfusion will no longer be possible.
- At their own request
- At the specific request of the Investigator (eg detection of a new significant safety concern related to the study drug).
- Occurrence of intercurrent diseases which in investigator's opinion, continuation of the study drug would be harmful to the subject's well-being.
- Pertinent non-compliance with the conditions for the trial or instructions by the investigator.
- Lost to follow up

Any subject removed from the study will remain under medical supervision until the condition is medically acceptable. Study subjects removed from the study will be replaced by enrolling another volunteer with similar demographic

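### The last scheduled antibody test (Visit 10, Day 125-150) can precede the protocol's own 4-5 month onset after the first infusion, and falls before month 4 after the second

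*Combined protocol and SAP*

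**What the plan says.** Section 2.3.3 calls antibody formation the main safety concern of the method. It cites 3 positive subjects among 20 adults (15%) and gives the timing: "The anti-BioRBC antibodies appeared 4-5 months after the infusion of BioRBCs". Activity disappeared 1-4 months after it was first detected.

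The infusions are on Day 5-7 and Day 35-42 after donation (Section 2.3.2). Section 2.3 puts the biotin dose at about 27.5 µg for the first and 5.5 µg for the second.

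The Synopsis states the purpose of the last visit: "On Day 125-150 post blood donation, subjects will be followed to evaluate anti-biotinylated RBC antibody formation". Section 2.2.2 describes Visit 10 as "scheduled between approximately 125-150 days, approximately 3-4 months post 2" (the second transfusion). Section 2.3.4 repeats the sampling days after Day 0: "On Day 32-41 and Day 125-150, plasma samples will be obtained from the subjects". The visit schedule and Appendix A add an antibody test at Visit 8: "This visit will be scheduled between approximately 65-72 days". No antibody test is scheduled after Visit 10. The additional blood draws at the end of Section 2.2.2 are for biotinylation analysis.

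Section 6.1 addresses the antibody risk by screening and by dose: "a lower dose of biotin will be used throughout this study compared to the previous study". For a subject found positive after the first infusion, Section 6.4.8 says: "The participant will be followed for signs and symptoms of hemolysis as well as the disappearance of the anti-biotinylated RBC antibodies".

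**The concern.** A single plasma test finds only antibodies that are already present. The Visit 10 window opens about when the cited onset period begins and closes before that period ends, counting from the first infusion. Counting from the second, it closes before the period begins. Section 2.3 itself expects that the two infusions "will result in exposure to BioRBCs for 5-6 months (approximately 165 days"), so the last test is taken while labelled cells from the second infusion can still circulate.

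Two things are at stake. A subject who turns positive after Visit 10 is never identified and so is not followed until the antibody disappears. And the observed antibody rate is lowered by timing as well as by any true effect of the lower dose, so it cannot be read directly against 15%.

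**Working it through.** **Inputs.** First infusion Day 5-7 and second Day 35-42 (Section 2.3.2). Visit 8 Day 65-72 and Visit 10 Day 125-150 (Section 2.2.2). Onset 4-5 months after infusion (Section 2.3.3), which is 120-150 days with 30-day months or about 122-152 days with calendar months (30.44 days).

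**The plan's own figure.** Visit 10 after the second infusion: 125 − 42 = 83 to 150 − 35 = 115 days, or 2.7-3.8 calendar months. This agrees with the stated 3-4 months.

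**Visits after the first infusion.**
- Visit 8: 65 − 7 = 58 to 72 − 5 = 67 days, far too early to cover the onset period.
- Visit 10: 125 − 7 = 118 to 150 − 5 = 145 days, or 3.9-4.8 months.
- Visit 10 moved to Day 150-160: 150 − 7 = 143 to 160 − 5 = 155 days.

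**Share of first-infusion antibodies present at the visit.** Assume visit days are even over the window and infusion days even over Day 5-7. The mean gap d is 137.5 − 6 = 131.5 days now and 155 − 6 = 149 days after the move.

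1. *Onset even over 4-5 months.* The share is the average of (d − start)/length, limited to 0-1.
   - Now: (131.5 − 120)/30 = 0.38 with 30-day months. With calendar months, (131.5 − 121.75)/30.44 = 0.32, or 0.33 once negative values are set to zero.
   - Moved: simulation with the limits applied gives 0.94 (30-day) and 0.89 (calendar). If every antibody lasted exactly one month, 0.91 and 0.88.
   - Within the current window the share runs from 0 at 118 days to 0.76-0.83 at 145 days.
2. *The phrase is rounded and means 3.5-5.5 months.* Calendar months: (131.5 − 106.5)/60.9 = 0.41 now and (149 − 106.5)/60.9 = 0.70 moved. With 30-day months: (131.5 − 105)/60 = 0.44 and (149 − 105)/60 = 0.73.
3. *The cited times are first detection, and true onset was 0-1 month earlier (even).* By simulation, 0.74-0.78 now and 0.99 moved.
4. *Extremes within months 4-5.*
   - All onset at month 4: 88-96% now, about 99% moved.
   - All at mid-period: 28-36% now, 100% moved.
   - All at month 5: 0% now, about 20-40% moved.
   - All at month 4 and all lasting exactly one month: 88-96% now, about 60-80% moved. In this case the current window is better.

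**Second infusion.** The current gap of 83-115 days never reaches 120, so no antibody appearing at 4-5 months would be found. Moved, the gap is 150 − 42 = 108 to 160 − 35 = 125 days, and the share found is only about 0-1%.

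**Illustration only.** If 15% still applied and onset were even over 4-5 months, Visit 10 would show 15% × 0.33 = 5.0% to 15% × 0.38 = 5.7% from the first infusion.

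**The case against.** The strongest reply is that a month-level phrase from 3 subjects is being read to the day. At 3.9-4.8 months, Visit 10 already matches the cited timing about as closely as that timing is stated. The cited report may also give first detection rather than onset. Its sampling schedule is not in the documents, and persistence is counted from detection. On that reading the current window could find about three quarters. This stands. A reader might infer that Visit 10 will find a third of antibodies and the later window nine in ten. The documents do not support that as an expected detection rate; it is one case among several. The direction is firmer than the size: the later window does better in every case above except the last under item 4.

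A reader might also infer that safety or an endpoint is compromised. The text does not support this. The cited antibodies were transient, did not affect recovery or survival, and caused no health problems. Neither infusion waits on Visit 10, because the test that gates the second infusion is Visit 5. The plan sets up no comparison with 15%, and Section 6.1 expects a lower dose, so the 5.0-5.7% illustration is not a forecast.

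Finally, the move does little for the second infusion, and most visits at Day 150-160 would still be under 120 days after it. That is correct and limits what the change can claim.

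**Conclusion.** The point holds as a scheduling weakness of modest consequence. On the protocol's own timing, the last antibody test can come before onset for the first infusion and always comes before month 4 for the second. Neither Visit 8 nor the optional draws fill the gap, so a negative Visit 10 result is not evidence that no antibody formed.

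For the first infusion the gain from Day 150-160 is 33-38% to 89-94%, about 41% to 70%, or about 74% to 99%, depending on how the 4-5 months are read. These shares assume visits spread evenly over the window and that the timing seen in 3 earlier subjects carries over to a lower dose. The conclusion does not extend to antibodies provoked by the second infusion, which the later window would also miss almost entirely.

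**What to change.** Move the existing Visit 10 from Day 125-150 to Day 150-160 in the Synopsis (Study Design), Section 2.2.1, Section 2.2.2 (Visit 10), Section 2.3.4 and Appendix A. The description relative to the second transfusion can stay, since 108-125 days is still roughly 3-4 months.

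Add to Section 2.3.4: *Antibody results will be reported with days since each infusion. The observed rate will not be compared directly with the 15% of the earlier study. The final test is timed to the first infusion and does not cover antibodies that appear 4-5 months after the second.* The reporting rule also covers anyone already tested in the current window. If the sponsor wants cover for the second infusion, that needs a further scheduled sample, near Day 185-195.

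Costs:
- There is no new visit or assay, but protocol and consent wording change.
- The window narrows from 26 to 11 days (Visits 8 and 9 have 8), which may produce more out-of-window visits.
- Follow-up ends somewhat later but within the stated 8 months: 28 days from Visit 1 to donation plus 160 is 188 days, against about 240.
- The fresh-blood survival draw moves from 118-145 to 143-155 days. It is outside the primary endpoint, and only about 4% of current draws fall at or before 120 days (on average Day 125-126 of a 25-day span, 1/25). If a 120-day fresh-blood value is wanted, an optional additional draw could supply it, and that would be an extra draw.
- The stored-blood draw moves from 83-115 to 108-125 days, which brackets the 120-day survival used in Section 2.5.3.
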